4.1. Sample Size

A total of 300 subjects will be globally assigned at 2:2:1:1 allocation ratio and receive BPZE1 nasal administration with placebo IM or Boostrix IM with placebo nasal administration on Day 1 and BPZE1 or placebo intranasal administration on Day 85. This sample size is based on clinical considerations but not a statistical power analysis as the study does not test any formal null hypothesis. **Table 4-1** presents the width of 95% CI for selected certain sample sizes under response rate assumptions (defined based on nasal mucosal immunogenicity) between 50% and 90%. Calculations were performed using PASS v12.

Table 4-195% Confidence Interval and Width for Selected Response Rate Assumptions for Relevant Treatment Arm Sample Sizes

Response Rate (%)	N = 50		N = 100		N = 200		N = 250	
	CI (%)	Width (%)						
50	35.5, 64.5	28.9	39.8, 60.2	20.3	42.9, 57.1	14.3	43.6, 56.4	12.7
60	45.2, 73.6	28.4	49.7, 69.7	19.9	52.9, 66.8	14.0	53.6, 66.1	12.5
70	55.4, 82.1	26.7	60.0, 78.8	18.7	63.1, 76.3	13.1	63.9, 75.6	11.7
80	66.3, 90.0	23.7	70.8, 87.3	16.5	73.8, 85.3	11.5	74.5, 84.8	10.3
90	78.2, 96.7	18.5	82.4, 95.1	12.7	85.0, 93.8	8.8	85.6, 93.4	7.8

Abbreviation: N, sample size.

Note: As described in the study design section, 200 subjects will receive a primary vaccination and 100 out of those 200 subjects will receive a boosting vaccination. In addition, 50 out of 100 active control subjects will receive a BPZE1 boost.

4.2. Randomization and Blinding

Subjects will be randomly assigned to 1 of 4 treatment arms, in a 2:2:1:1 ratio, as presented in Table 3-1. No stratification factors will be used in the randomization. An interactive response technology will be used to administer the randomization schedule centrally. Biostatistics will generate the randomization schedule using SAS® software Version 9.4 (SAS Institute Inc, Cary, North Carolina) for the interactive response technology, which will link sequential subject randomization numbers to treatment codes. The randomization schedule will be created by the dedicated randomization team, stored in a separate project area, and will be blinded to the project team with the exception of the unblinded pharmacy staff who will manage vaccine logistics, preparation, and administration, but will not be involved in study-related assessments or have subject contact for data collection following study vaccine administration.

This is an observer-blinded study. To maintain the blind, placebo vaccination via intranasal and IM routes will be included and unblinded pharmacy staff will manage vaccine logistic, preparation, and administration (when necessary) so as to maintain the blind from the remainder of the study personnel and subjects. The pharmacy staff will not be involved in study-related assessments or have subject contact for data collection following study vaccine administration.

A subject's treatment assignment will not be broken until the end of the study for the clinical site study team unless medical treatment of the subject depends on knowing the study treatment the subject received. In the event that the blind needs to be broken because of a medical emergency, the investigator may unblind an individual subject's treatment allocation.

As soon as possible, the investigator should first contact the medical monitor to discuss the medical emergency and the reason for revealing the actual treatment received by that subject. The treatment assignment will be unblinded through interactive response technology. Reasons for treatment unblinding must be clearly explained and justified in the electronic case report form (eCRF). The date on which the code was broken together with the identity of the person responsible must also be documented.

4.3. Analysis Set

4.3.1. Intent-to-Treat (ITT) Analysis Set

The Intent to Treat Analysis Set will consist of all subjects who have been randomized to the study. Subjects will be classified according to the study group randomized. The data of subject disposition, demographics, and medical history will be summarized on this analysis set.

4.3.2. Immunogenicity Analysis Set

The Immunogenicity Analysis Set will include all the Intent to Treat subjects who received the prime dose of the study vaccine(s) and have contributed both pre- and at least 1 post prime vaccination sample (mucosal or serum immunogenicity testing, respectively) for which valid results were reported and who have not received any component of a licensed pertussis vaccine in the 5 years through Day 113 of the study. Subjects will be classified according to the study vaccine received. For analysis of boosting, those subjects who have received all vaccinations and have a pre (Day 78 for mucosal and Day 85 for serum) and a post boost immune sample (Day 113) for which valid results were reported will be utilized. Additional testing for maximum response will be assessed for those subjects who received all vaccinations and have both a baseline sample (screening or Day 1 depending on the sample type) and a sample at Day 113. Immune persistence will be assessed in those subjects who contribute to sampling at Days 169 and 254.

Subjects will be classified according to the study vaccine received and according to humoral and mucosal immunity samples as described. Subjects who discontinued from study will be classified according to randomized treatment arm. Subjects who missed a boost dose, will be classified to no boost treatment arm based on prime arm. Subjects who received wrong vaccination by mistake and discontinued from study will be classified according to actual vaccination, priority higher.

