3.1. Overall Study Design and Plan

This is a multi-center, randomized, placebo-controlled, and observer-blinded trial with a 6-month safety follow-up after the last vaccination. After signing the informed consent form (ICF), subjects will be enrolled in the trial and screened over a window of 30 days; screening will include obtaining a nasal sample for mucosal pertussis immune status. Subjects will also be asked to provide a signed ICF for the use of samples for further pertussis-specific testing or assay development. On Day 1, eligible subjects will be randomized to 1 of 4 treatment arms and receive BPZE1 intranasal vaccine or formulation buffer for injection (placebo) (via the VaxINator atomization device) and a licensed aP comparator vaccine (ie, Boostrix) or sterile normal saline (placebo), given by IM injection. To maintain the blind throughout the trial period, placebo vaccination via intranasal and IM routes, using formulation buffer and normal saline, respectively will be included, and unblinded pharmacy staff will manage vaccine logistics, preparation, and (if needed) administration but will not be involved in study-related assessments or have subject contact for data collection after study vaccine administration. Approximately 300 subjects will be randomly assigned 2:1 for the first (prime) vaccination with 200 subjects assigned to BPZE1 vaccination and 100 subjects assigned to Boostrix (aP vaccine) vaccination. During the second (boosting) vaccination, half of each of the treatment groups will be further randomly assigned to receive BPZE1 or placebo resulting in a 2:2:1:1 randomization scheme (Table 3-1).

Table 3-1 Dosing Scheme

Treatment Arm	Day 1				Day 85	
	Nasal Vaccination		IM Vaccination		Nasal Vaccination	
	BPZE1	Placebo ^a	Boostrix	Placebo ^b	BPZE1	Placebo ^a
A (N = 100)	X	-	-	X	X	-
B (N = 100)	X	-	-	X	-	X
C (N = 50)	-	X	X	-	X	-
D (N = 50)	-	X	X	-	-	X

Abbreviation: IM, intramuscular.

^a Intranasal application of 2×0.4 mL (0.4 mL per nostril) placebo (formulation buffer).^b IM injection of 0.5 mL placebo (normal saline) to the deltoid region.

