The dose of BPZE1 active ingredient will be administered to the subject within 60 minutes of removal from the freezer. One milliliter of WFI will be used to reconstitute the 1 mL vial of lyophilized BPZE1, but only 0.8 mL of vaccine will be withdrawn for administration into both nostrils. Following reconstitution, the VaxINator will be attached to the syringe, and 0.4 mL volume will be administered to each nostril. In the case of placebo nasal vaccination, a similar volume of WFI will be reconstituted into a vial containing only lyophilized buffer, followed by 0.4 mL volume administered into each nostril with the vaccinator. The VaxINator provides a uniform, controlled delivery, which allows the vaccinator to accurately deliver 0.4 mL of vaccine to the initial nostril and then administer the remaining 0.4 mL to the opposite nostril.

The study vaccine will be labeled according to manufacturer specifications and include the statement “Caution: New Drug – Limited by Federal Law to Investigational Use.”

4. General Statistical Considerations

No formal hypothesis will be tested in this study. Statistical analysis will be performed using SAS software Version 9.4. Continuous variables will be summarized using the mean, 2-sided 95% CI of the mean, SD, median, minimum value, and maximum value. Categorical variables will be summarized using frequency counts and percentages, as well as 2-sided 95% CI for proportions computed using the Clopper-Pearson method. Graphics of reverse cumulative distribution of anti-pertussis antibody titers will be generated through Day 113 for the primary database lock and assessing serum and mucosal pertussis antigen response. .

For summary precision, mean and median will have one more decimal place than the reported value, SD will have two more decimal places than the reported value, minimum and maximum will have the same decimal place as the reported value. Percentages and 95% CI will have one decimal place.

Where applicable, data analyses will be conducted for the prime period (prior to boosting) and boost period (at or post boosting). Pre-prime and pre-boost baseline will be used for summaries based on the Immunogenicity Analysis Set.

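### SAP 4.3.2 moves subjects who miss the boost but stay in follow-up into the control arms for the Day 113 primary summary, and its licensed-vaccine clause makes no exception for study Boostrix

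*SAP*

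**What the plan says.** SAP 4.3.2 contains three rules that bear on this point.

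- **Missed boost.** "Subjects who missed a boost dose, will be classified to no boost treatment arm based on prime arm". Protocol 7.7.1 labels B and D as the no-boost arms, so the rule sends A to B and C to D. The neighbouring sentence keeps subjects who discontinue the study in their randomised arm. No priority is given when both apply.
- **Boosting analysis.** "For analysis of boosting, those subjects who have received all vaccinations and have a pre (Day 78 for mucosal and Day 85 for serum"; the sentence goes on to require a valid Day 113 sample.
- **Licensed pertussis vaccine.** The set admits only subjects "who have not received any component of a licensed pertussis vaccine in the 5 years through Day 113 of the study". Protocol 7.5 has the same clause. SAP 3.1 describes the Day 1 injection in C and D as "a licensed aP comparator vaccine (ie, Boostrix").

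SAP 8.1 summarises the primary endpoint, mucosal seroconversion at Day 29 or Day 113, on the Immunogenicity Analysis Set with no further restriction. The only sensitivity analysis (SAP 8.3) uses the Per Protocol set, which is drawn from the same set and grouped by vaccines actually received (SAP 4.3.3).

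**The concern.** Arms A and B share the same prime and differ by random allocation of the Day 85 dose; so do C and D. These contrasts are the randomised evidence on what the boost adds. A missed boost is a post-randomisation event. Protocol 4.2.1 lists adverse events, intercurrent illness, pregnancy and disallowed substances as reasons to stop vaccination, and some of these could be related to immune response. Protocol 4.2.2 keeps such subjects on the visit schedule, so they can supply a Day 113 sample.

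The transfer runs one way. Subjects in B who miss their placebo dose stay in B, so A loses its missed-boost subjects while B holds those of both arms. The moved subjects also received nothing on Day 85, whereas B and D received intranasal placebo, so B and D would no longer be the placebo-boost groups that were randomised. No immunogenicity table by randomised arm is planned that would show the effect.

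The licensed-vaccine clause raises a different problem: a rule defining the primary-endpoint set cannot be programmed as written without removing the comparator.

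**Working it through.** **Inputs from the documents.** SAP 4.1: "A total of 300 subjects will be globally assigned at 2:2:1:1 allocation ratio", that is 300 × 2/6, 2/6, 1/6, 1/6 = 100, 100, 50, 50. These are nominal sizes and include the 24 lower-dose lead-in subjects whom SAP section 4 presents separately. SAP section 4: "2-sided 95% CI for proportions computed using the Clopper-Pearson method".

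**The plan's own figure.** Exact limits from beta quantiles reproduce all 20 cells of SAP Table 4-1 (Protocol Table 7-1) to within 0.05 points. Example, 80% at N = 50: 66.28 to 89.97, width 23.69, against 66.3, 90.0 and 23.7 in the table.

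**Assumptions, since the documents give neither figure.** The missed-boost rate m in A and C is 2%, 5% or 10%, all of whom stay in follow-up with a valid Day 113 sample. The Day 113 response of moved subjects differs from the rest of B by d = 20 or 40 points.

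With k = m × n moved, their share of the control arm is k/(n + k), and the control proportion shifts by k × d/(n + k) = m × d/(1 + m).

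| m | A / B after move | C / D after move | Moved share of B | Shift in B, d = 20 | Shift in B, d = 40 |
|---|---|---|---|---|---|
| 2% | 98 / 102 | 49 / 51 | 2/102 = 2.0% | 0.4 | 0.8 |
| 5% | 95 / 105 | 48 / 52 | 5/105 = 4.8% | 1.0 | 1.9 |
| 10% | 90 / 110 | 45 / 55 | 10/110 = 9.1% | 1.8 | 3.6 |

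(At 5%, C gives 2.5 subjects, taken as 2.) Check of the 10% row with B at 60% and moved subjects at 40%: (100 × 0.60 + 10 × 0.40)/110 = 58.2%, a shift of 1.8 points.

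**Effect on the contrast.** Suppose the boost has no effect, 10% miss the Day 85 dose in both A and B, and those dosed seroconvert at 60%.

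- Missed-dose subjects at 40%. As randomised, both arms read (90 × 0.60 + 10 × 0.40)/100 = 58%. After relabelling, A reads 54/90 = 60% and B reads (54 + 20 × 0.40)/110 = 56.4%, a spurious difference of +3.6 points.
- Missed-dose subjects at 80%. As randomised, both read (54 + 8)/100 = 62%. After relabelling, A reads 60% and B reads (54 + 16)/110 = 63.6%, a difference of −3.6 points.

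So the sign depends on how these subjects respond, which the documents do not tell us. Restricting both arms to fully vaccinated subjects gives 60% and 60% in either case.

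**Licensed-vaccine clause read literally.** 300 − 100 = 200 subjects remain: A 100, B 100, C 0, D 0. No Boostrix proportion or interval can be computed, and the Per Protocol set inherits this. With study Boostrix exempted, up to 300 remain, and Table 4-1 gives widths at 80% of 16.5 points for C+D (N = 100) and 23.7 for C or D alone (N = 50). Protocol 7.7.1 plans immunogenicity summaries for C+D, C and D, so the clause and that section cannot both stand as worded.

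**The case against.** The strongest case on the other side has five parts.

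1. *The all-vaccinations restriction already solves it.* It does for the boosting analysis, and a reader who infers that the 2-fold boost results are contaminated would be wrong. One could argue that the restriction also covers the Day 113 primary summary, because Protocol 7.7.1 refers to a separate Boost Immunogenicity Analysis Set. But SAP 8.1 names the undivided set without qualification, and if the restriction reached every Day 113 by-arm summary the relabelling sentence would have little left to act on. Persistence at Days 169 and 254 is not restricted to fully vaccinated subjects either.
2. *The rule only spells out classification by vaccine received, which Protocol 7.5 already sets.* Partly so: the principle is in the protocol and the detail is left to the SAP. The explicit missed-boost rule is nevertheless an SAP addition, while SAP section 11 declares no changes.
3. *The effect is small and the study is descriptive.* "No formal hypothesis will be tested in this study", and "This sample size is based on clinical considerations but not a statistical power analysis". The largest shift in B at a 20-point gap, 1.8 points, compares with an interval width of 19.9 at 60% and N = 100. This stands, and it limits the severity.
4. *Few subjects are affected.* Those who leave the study keep their randomised arm, a scheduled visit does not guarantee a sample, and acute respiratory illness is a temporary exclusion with a booster window, so it may only delay the dose. This stands. The clear case is a subject who misses the boost, remains in follow-up and gives a valid Day 113 sample.
5. *The licensed-vaccine clause plainly means non-study vaccine.* It mirrors exclusion criterion 1, and Protocol 5.7 records non-study vaccines separately. This stands as to intent; the text still needs the exception.

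**Conclusion.** The concern holds in limited form. As written, SAP 4.3.2 with SAP 8.1 lets subjects who miss the boost but stay in follow-up leave A or C and be counted in B or D for the Day 113 primary summary. The shift in B is 0.4 to 1.8 points at 2% to 10% missed and a 20-point gap, both assumed.

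Three stronger readings are tempting and not supported:

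- That the rule inflates the apparent boost benefit. This needs missed-boost subjects to respond less well, which nothing in the documents shows.
- That the trial will lose its Boostrix comparator. Protocol 7.7.1 shows that C and D are meant to be analysed, so this is a drafting error in SAP 4.3.2 and Protocol 7.5.
- That missed boosts would be invisible. The compliance table on the ITT set (SAP 7.2.1) reports receipt of the boost by arm, and ITT also serves baseline characteristics and prior medications. What is absent is any immunogenicity result by randomised arm.

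This should be fixed, but it does not threaten the trial as a whole.

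**What to change.** (a) In SAP 4.3.2, replace the missed-boost sentence with a rule that such subjects are never counted in another randomised arm, and state that it overrides the general rule of classifying by vaccine received. Deleting the sentence alone would not be enough, because the general rule could still place unboosted subjects under the no-boost label. State also that the Day 113 by-arm summaries in SAP 8.1 use the same all-vaccinations restriction as the boosting analysis.

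(b) That restriction still drops selected subjects. Add one table of Day 113 seroconversion by randomised arm, using all subjects with valid baseline and Day 113 samples.

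(c) In SAP 4.3.2 and Protocol 7.5, reword the clause to exclude *any licensed pertussis vaccine other than Boostrix given as study vaccine*. The word *given* matters: an exception for assigned Boostrix only would exclude a subject who received it in error, whom SAP 4.3.2 may classify by actual vaccination.

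Cost: a few sentences, one extra table, and a few fewer subjects in the B and D columns.

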4.3.3. Per Protocol (PP) Analysis Set

The Per Protocol Analysis Set will include all subjects in the Immunogenicity Analysis Set, with the following exclusions:

- Data from all available visits for subjects following the receipt of unsuitable investigational product (either via dispensed/assigned or delivered).
- Data from all available visits for subjects found to be ineligible at baseline per Protocol Version 6.0.
- Data from all visits for subjects following the use of major immune-modulators, immune suppressants, receipt of blood products, or use of forbidden nasal solutions (eg, sprays, washes, neti pot) from 30 days prior to Day 1 through Day 113.
- Data from all visits for subjects following clinically significant protocol deviations that can affect the efficacy (immunogenicity) results.

- Data from any visit that occurs substantially out of window as defined by exceeding 30 days past the visit window or the time point whereby the follow-on visit should have occurred, whichever is most restrictive. Standard visit windows are described in schedule of events (Appendix 13.1).

For analyses using the Per Protocol Analysis Set, subjects will be grouped based on study vaccines actually received.

4.3.4. Safety Analysis Set

The Safety Analysis Set will consist of all subjects who have received at least 1 dose of the study vaccine and have any safety data available. Subjects will be classified according to the vaccine received. The primary safety analysis will be done on this analysis set.

4.3.5. Safety Lead-in Analysis Set

The Safety Lead-in Analysis Set will consist of the first 48 subjects who have been randomized to the study. Subjects will be classified according to the vaccine received and group into BPZE1 prime (10^7 CFU), BPZE1 prime (10^9 CFU) and Boostrix prime arms

4.4. Analysis Periods

Safety data will be summarized by analysis period as outlined below.

- Prime Period:

This period starts on the day of primary vaccination (prime dose) at Day 1/Visit 1 and ends on either: (1) the day prior to second vaccination (boost dose) on Day 85/Visit 5 for those who received a boosting dose; or (2) the day of early termination visit if the subject discontinued before Day 85/Visit 5; or (3) the last known study day if the subject is lost to follow-up prior to Day 85/Visit 5.

- Boost Period:

This period starts on the day of boosting vaccination (boost dose) at Day 85/Visit 5 and ends on either: 1) the day of Day 113/Visit 8; or 2) the day of the discontinuation visit if the subject discontinued prior to or at Day 113/Visit 8; or 3) the last known study day if the subject lost to follow-up prior to Day 113/Visit 8.

- Long term safety follow-up:

This period starts at the next day after Day 113/Visit 8 or discontinuation visit and stops at the last follow-up visit or the last assessment date.

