6.3.4 Clinical Safety Laboratory Tests

Clinical safety laboratory tests will include the following and will be collected as mentioned in the schedule of events for all subjects at screening and for the safety lead-in cohort at screening, and Days 8, 85 (prior to vaccination), and 92 (Table 13-1):

- Hematology: hemoglobin, white blood cell count and differential, and platelet count.
- Chemistry panel: sodium, potassium, glucose (random), blood urea nitrogen, creatinine, calcium, albumin, total protein, bilirubin, alanine aminotransferase, and aspartate aminotransferase

- Coagulation: Prothrombin time/international normalized ratio and partial thromboplastin time

For the full cohort, toxicity scoring of >1 for hemoglobin, white blood count, platelets, creatinine, alanine aminotransferase, aspartate aminotransferase, bilirubin, prothrombin time and partial thromboplastin time will be used as exclusionary criteria (Table 13-2). For the safety cohort all laboratory tests noted in Table 13-2 with toxicity score >1 will be used as exclusionary criteria. For the safety cohort being followed with additional scheduled safety labs, should any laboratory value result in a grade 3 or greater toxicity score this lab must be entered as an adverse event and followed with retesting and observing for resolution or new clinical baseline. In the case of an alternative explanation for the abnormal laboratory (eg, urinary tract infection with an elevated WBC) the illness should be the AE classification. Investigators should determine if any laboratory values resulting in a grade 2 toxicity score should be entered as an AE, with repeat testing based on clinical judgement and the laboratory value of concern.

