9.2. Unsolicited Adverse Events

Unsolicited Adverse events will be coded according to Medical Dictionary for Regulatory Activities (MedDRA) version 22.0 or above. Unless otherwise specified, unsolicited AEs will be summarized by System Organ Class (SOC) and Preferred Term (PT), with SOCs sorted in the alphabetical order and PTs within each SOC in descending order of subject incidence. Partial missing unsolicited adverse event start dates will be imputed based on Appendix 13.4.

TEAE is defined as an AE that starts or an existing AE that worsens on or after the date of prime vaccination. AE will be summarized by period, including Day 1 to Day 84, Day 85 to Day 113, and Day 114 to End of Study (EOS). From Day 1 to Day 29, all AE regardless causality will be recorded and summarized. From Day 30 to Day 84, all AE related to vaccination and SAE will be recorded and summarized. From Day 85 to Day 113, all AE regardless causality will be recorded and summarized. From Day 114 through end of study (EOS), all SAE will be recorded and summarized.

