9.3. Clinical Laboratory Evaluations

For those subjects in the Safety lead-in analysis set, laboratory results will be summarized for serum chemistry, hematology and coagulation as observed values and change from baseline on Day 8/Visit 2 following prime vaccination and Day 92/Visit 6 following boost vaccination using descriptive statistics (mean, median, standard deviation, min, max). Laboratory results will also be classified by toxicity score based on the US Food and Drug Administration (FDA) toxicity scoring system (Appendix 13.2). Counts and percentages of subjects will be summarized by toxicity grade on Day 8 and 92. In the case of no toxicity classification the score of 0 will be assigned.

For those subjects in the safety set, baseline value will be summarized for serum chemistry, hematology and coagulation using descriptive statistics (mean, median, standard deviation, min, max).

Summaries will be presented based on treatment arms of BPZE1 prime with BPZE1 boost (A), BPZE1 prime with no boost (B), Total Post BPZE1 (A+B), Boostrix prime with BPZE1 boost (C) and Boostrix prime with no boost (D), Boostrix prime (C+D), Total Post Booster BPZE1 (A+C), and Total Post Placebo Boost (B+D), Total Any BPZE1 Exposure (A+B+C) and Total (A+B+C+D).

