9.3.1. Hematology

Hematology will be collected at screening for all screened subjects, and at Visit 2 Day 8, Visit 5 Day 85 prior to vaccination, and Visit 6 Day 92 for the Safety Lead-In Analysis Set. Hematology tests will include hemoglobin, white blood cell count and differential, and platelet count.

A by-subject listing will also be provided.

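### The SAP divides prime from boost by calendar day, so a Grade 3 laboratory event from the lead-in cohort's pre-dose Day 85 sample is counted in the boost period

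*SAP*

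**What the plan says.** **Periods.** SAP 4.4 opens with its scope: "Safety data will be summarized by analysis period as outlined below". For boosted subjects the prime period ends on "the day prior to second vaccination (boost dose) on Day 85/Visit 5 for those who received a boosting dose". For the boost period: "This period starts on the day of boosting vaccination (boost dose) at Day 85/Visit 5 and ends on either" Visit 8, a discontinuation visit or the last known study day.

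**Adverse events.** SAP 9.2 uses day ranges: "AE will be summarized by period, including Day 1 to Day 84, Day 85 to Day 113, and Day 114 to End of Study (EOS"). Treatment emergence looks only at the first dose: "TEAE is defined as an AE that starts or an existing AE that worsens on or after the date of prime vaccination". SAP 9.2.1 gives the TEAE overview separately for the prime and boost periods. SAP section 9 sets the boost-period columns: each arm, A+C as the total after a BPZE1 boost, and B+D as the total after a placebo boost.

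**Laboratory.** SAP 9.3.1 schedules hematology at "Visit 2 Day 8, Visit 5 Day 85 prior to vaccination, and Visit 6 Day 92 for the Safety Lead-In Analysis Set"; 9.3.2 and 9.3.3 put chemistry and coagulation on the same schedule. Protocol 6.3.4 requires for the safety cohort that "should any laboratory value result in a grade 3 or greater toxicity score this lab must be entered as an adverse event", and Protocol 6.3.5.4 and 6.6 repeat the rule. Where an illness explains the value, 6.3.4 and 6.6 have the illness entered instead. For the grade tables, SAP 9.3 states: "Counts and percentages of subjects will be summarized by toxicity grade on Day 8 and 92".

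**General wording.** SAP section 4 and Protocol 7.7 describe the prime period as what comes before boosting and the boost period as what comes at or after it.

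**The concern.** A scheduled procedure falls on the wrong side of the cut. The Day 85 safety sample is always pre-dose, yet an event dated to it carries the boost date. The day-based rule therefore counts it after the boost, under columns that present it as following BPZE1 or placebo. The boost cannot have caused it.

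The grade tables cover Days 8 and 92 only, so no laboratory summary shows that the abnormality came first. A reader would have to find that in the by-subject listings. What is at stake is the accuracy of the boost-period unsolicited-event counts for a small number of subjects.

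**Working it through.** The plan has no figure to reproduce here; the question is how the stated rules classify an event.

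**1. Apply both rules.** SAP 4.4: prime if onset is no later than boost day minus 1, otherwise boost (up to Visit 8). SAP 9.2, read as study days: Day 1–84 or Day 85–113. The schedule of events allows the boost visit +10 days, so Day 95 is the late case.

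| Boost given | AE onset | SAP 4.4 | SAP 9.2 |
|---|---|---|---|
| Day 85 | Day 84 | prime | Day 1–84 |
| Day 85 | Day 85, pre-dose sample | boost | Day 85–113 |
| Day 95 | Day 94 | prime | Day 85–113 |
| Day 95 | Day 95, pre-dose sample | boost | Day 85–113 |

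The pre-dose finding is classed as boost under both rules. With a late boost the two sections also disagree about the day before it.

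**2. Look for text that corrects this.**
- The TEAE definition cannot remove the event, because it tests only the prime date.
- SAP Appendix 13.4 deals with incomplete dates only.
- SAP 9.1 ties events to the most recent vaccination, but for solicited reactions only.
- SAP 4.5 accepts a boost-day value taken before the dose as pre-boost baseline. The SAP thus separates same-day pre-dose data for baselines but not for adverse events.

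**3. Dating the event.** The documents do not say how the onset of a laboratory event is set. Samples go to a central laboratory (Protocol 6.7). The sample date and any later result date both give the boost period. Only an explaining illness with earlier onset would stay in the prime period.

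**4. Who is exposed.** The lead-in is 16 + 8 + 16 + 8 = 48 subjects. At 2:2:1:1 this gives A 16, B 16, C 8, D 8, so 24 are assigned a BPZE1 boost (12 per dose level) and 24 placebo.

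**5. Size of one misplaced event** in the specified tables (Safety Analysis Set, planned arm sizes):
- A: 1/100 = 1.0 point
- C: 1/50 = 2.0 points
- A+C: 1/150 = 0.67 point

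Arms B, D and B+D have the same sizes. SAP section 4 promises separate key safety output for the 24 subjects of the 10^7 CFU group, with reactogenicity and laboratory grading as its examples. If unsolicited events were included, one event among that group's BPZE1-boosted subjects would be 1/12 = 8.3 points.

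**6. Likelihood.** The documents give no rate. Assume a per-subject probability p of a Grade 3 or greater Day 85 result; the chance of at least one in n subjects is 1 − (1 − p)^n.

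| p (assumed) | Expected in 48 | At least one in 48 | At least one in the 24 assigned BPZE1 boost |
|---|---|---|---|
| 1% | 0.48 | 0.383 | 0.214 |
| 2% | 0.96 | 0.621 | 0.384 |
| 5% | 2.4 | 0.915 | 0.708 |

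**The case against.** Counting everything on the dose date as post-dose is a conservative convention, and the general wording does let the boost period begin at boosting. Boost allocation is randomized and observer-blinded, so pre-dose findings fall by chance under both BPZE1 and placebo boost. No hypothesis is tested. Events are also summarized by relatedness, and by-subject laboratory listings keep the sample visible. Lead-in subjects must be Grade 1 or lower at screening on every listed test, so Grade 3 results may be rare.

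Most of this stands. It means little comparative bias and a small effect. It does not make the count right: the convention helps when the order of event and dose is unknown, and here the protocol fixes the order.

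Stronger readings that a reader might infer, and why they fail:

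- **Shifts of 8 to 25 points across the lead-in.** These would need denominators of 12, 8 or 4. The SAP groups the Safety Lead-in Analysis Set by prime vaccine and dose, and its listed TEAE tables are the interim ones. No boost-period TEAE table is specified for the 10^9 CFU lead-in subjects. For the 10^7 CFU group a separate display is possible but not stated for unsolicited events.
- **A compromised laboratory endpoint or dose-advancement decision.** The grade endpoint is tabulated by visit on Days 8 and 92. The scheduled SMC review uses data through Day 8 after the prime and any events to that point. The period rule moves neither.
- **The same error on Day 1.** No safety laboratory sample is scheduled on Day 1. Protocol 6.3.5.4 restricts event collection before Day 1, and 6.3.5.5 treats conditions present at screening as baseline.
- **The same weight for examinations and vital signs.** Mandatory entry covers laboratory values only, and vital signs are recorded separately before and after the dose. A finding that delays the boost falls in the prime period under SAP 4.4.

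**Conclusion.** The point holds as a narrow classification error. By the SAP's own rules, a Grade 3 or greater value from the pre-dose Day 85 sample that is entered as an event in its own right becomes a boost-period TEAE. That conflicts with the general wording in SAP section 4.

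The damage is confined to descriptive unsolicited-event tables and, for laboratory events, to the 48 lead-in subjects. The sizes in the working assume full planned enrollment. The 8.3-point figure applies only if 10^7 CFU events are displayed separately. Whether any such event occurs is unknown; the probabilities rest on assumed rates. The correction is still worth making, because a stated rule gives a wrong count and the remedy is nearly free.

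**What to change.** In SAP 4.4 and 9.2, state that an adverse event identified from a sample or assessment that the protocol schedules before the Day 85 vaccination is assigned to the prime period, and that all other events with onset on the boost date stay in the boost period. Define the cut in both sections by the actual boost date, so that they agree when the boost is late.

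No onset clock time is needed, because the schedule already establishes the order. A general clock-time rule would be harder to apply: Protocol 6.3.5.5 lists the date of onset for unsolicited nonserious events, not the time.

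The cost is a short SAP edit and one programming flag linking the event to the pre-dose assessment. Same-day events not tied to such an assessment still default to post-boost, so some pre-dose events may remain there, but no post-dose event is moved out of view.
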